7.1. Study Design

This will be a prospective observational study. A convenience sample will be carried out to include 200 patients who attend the ENERI Medical Institute, La Sagrada Familia Clinic and Sanatorio Mendez with a clinical indication to be evaluated by a CCTA due to suspected CAD or known CAD. The study will have a baseline stage in which a clinical evaluation will be performed, blood samples will be drawn for transcriptome analysis and laboratory analysis. Then, a DNA sample obtained by swabbing the buccal mucose will be taken. Subsequently, the images obtained from the clinically indicated CCTA will be assessed to explore the outcomes of interest. At the end of patient enrollment, biological samples will be sequenced for in silico evaluation of the results. Finally, a 5-year follow-up will be carried out via telephone or email contact to collect data on the incidence of fatal and non-fatal cardiovascular events.

8. Study Population

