6.1 Primary Objective

The main objective of this study is to investigate the diagnostic accuracy of whole-blood transcriptome analyzed by artificial intelligence in detecting the presence and extent of coronary atherosclerosis in stable patients with suspected or known coronary artery disease (CAD), using coronary computed tomography angiography (CCTA) images.

Specific aims:

I) To classify patient transcriptomes based on the presence and extent of the following CCTA outcomes:

- Coronary calcium score
- Total coronary plaque burden
- Degree of coronary stenosis
- Coronary high-risk plaques (low-attenuation, positive remodeling; spotty calcification, or napkin-ring sign)

II) To train artificial intelligence algorithms using information from the transcriptome to recognize the outcomes of interest in the training set.

III) To explore the diagnostic accuracy (sensitivity and specificity) of the method in detecting the presence, absence, or extent of the outcomes of interest in the validation/test set.

6.2 Secondary Objectives:

The secondary objectives of this study are as follows:

6.2.1 To explore the diagnostic accuracy of whole-blood transcriptome in relation to other outcomes of interest provided by CCTA images, including:

- Presence and extent of aortic calcification
- Hepatic steatosis
- Flow limiting artery obstruction (coronary fractional flow reserve)
- Coronary artery inflammation (perivascular fat attenuation index)
- Total epicardial adipose tissue volume

6.2.2 To calculate the polygenic risk score (PRS) from the transcriptome and explore its association with the previously described outcomes of interest.

6.2.3 To explore the differences in transcriptomics of peripheral blood between patients who did and did not develop a cardiovascular event during follow-up.

7. Methods

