8.1. Inclusion Criteria

- Men and women between 18 and 75 years, with a clinical indication to be evaluated by a CCTA due to suspected or known CAD.
- Signature of informed consent.

8.2. Exclusion criteria.

- Previously known chronic renal or hepatic insufficiency.
- Active chronic lung disease, defined as: exacerbated asthma, exacerbated COPD, or pulmonary fibrosis.
- Myocardial infarction, unstable angina, cerebrovascular accident, or vascular interventions (any territory) in the past 6 months.
- Implantation of drug-eluting stents in the last 12 months.
- Revascularization surgery (By-pass)
- Indication of Angio-CT for congenital heart disease or Transcatheter Aortic Valve Replacement (TAVI)
- Presence/ diagnosis of heart failure symptoms or signs (ie. dyspnea, asthenia, edema) with objective evidence of pulmonary or systemic congestion at rest or with exercise in the last 6 months⁴³.
- Left ventricular ejection fraction <50% confirmed by objective diagnostic methods (eg doppler echocardiogram).
- Severe valvulopathies, confirmed by objective diagnostic methods (eg doppler echocardiogram).
- Uncontrolled hyper or hypothyroidism.

⁴³ "2013 ACCF/AHA guideline for the management of heart failure." <https://pubmed.ncbi.nlm.nih.gov/23741058/>. Accessed 10 Apr. 2023.

- Suprarenal insufficiency.
- Previous surgeries in the last 3 months.
- Severe trauma in the last 6 months, defined as one that involved bone fractures and/or surgical interventions.
- Known active cancer disease or under treatment (acute or preventive), or history of cancer disease without criteria for cure.
- Diagnosis of active autoimmune disease or any pathology under immunosuppressive treatment.
- Ongoing pregnancy, postpartum period of less than 12 months or breastfeeding.
- Other serious diseases with an estimated life expectancy of less than 12 months (according to the investigator's opinion).
- Temperature greater than 37.5°C recorded by a thermometer or any acute infection caused by viruses or bacteria confirmed by a health professional in the previous 30 days.
- Pacemaker/Cardio-Defibrillator Implantation.
- Prior to the study: heart rate > 70 l/m or atrial fibrillation or frequent extrasystoles that in the opinion of the specialist physician will affect the quality of the cardiovascular imaging.

9. Procedures

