9.1. Eligibility and informed consent

Patients referred to CCTA scans with a medical indication due to suspected CAD or known CAD, will be recruited at Clínica Sagrada Familia and Sanatorio Mendez in Buenos Aires. Patients who meet the eligibility criteria will be approached by the main investigator or one of the study collaborators and the characteristics of the procedure to be performed, the risks of the associated procedures and the scope of the research to be

carried out will be explained to them. After providing the necessary information and answering the patients' questions, and once they have expressed that they agree to donate blood samples, mucose DNA cells via oral swab, associated data and the CCTA resulting image to the study, they will be formally invited to sign the informed consent.

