10.5. Analysis plan

For the description of the general characteristics of the study population, descriptive statistics such as means, medians and proportions will be used. To calculate the diagnostic performance of the method, the following will be calculated:

- True Positives (TP) or the probability that the test is positive since the disease is present
- True Negatives (TN) or the probability that the test is negative since the disease is not present.
- False Positives (FP) or Type I Error
- False Negatives (FN) or Type II Error
- Sensitivity: $VP/VP+FN$
- Specificity: $VN/ VN+FP$
- Precision or accuracy: $VP/VP+FP$ or sensitivity + (1-specificity)

The accuracy can vary between 0.5 and 1, where 1 represents a perfect diagnostic value and 0.5 is a test without diagnostic discriminatory capacity. An area under the curve (AUC) will also be performed to determine the diagnostic capacity of the trained algorithm.

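### A convenience sample, with no rule to invite every eligible CCTA referral and no log of those not enrolled, leaves open whether the accuracy estimates carry over to all stable patients referred for CCTA.

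*Protocol*

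**What the plan says.** **Target of the estimate.** Section 6.1 sets the primary objective as diagnostic accuracy of the whole-blood transcriptome "in stable patients with suspected or known coronary artery disease (CAD), using coronary computed tomography angiography (CCTA) images".

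**How patients enter.** Section 7.1 names the sampling method: "A convenience sample will be carried out to include 200 patients". Section 8.1 admits men and women of 18 to 75 years "with a clinical indication to be evaluated by a CCTA due to suspected or known CAD". On recruitment, section 9.1 says: "Patients who meet the eligibility criteria will be approached by the main investigator or one of the study collaborators". It does not say whether all of them are approached, in what order, or whether those missed or refusing are recorded.

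**Order of events.** Section 7.1 opens with "This will be a prospective observational study". At baseline, "blood samples will be drawn for transcriptome analysis and laboratory analysis", and then: "Subsequently, the images obtained from the clinically indicated CCTA will be assessed to explore the outcomes of interest".

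**What is reported.** Section 10.5 begins: "To calculate the diagnostic performance of the method, the following will be calculated". It lists sensitivity, specificity and the ratio VP/(VP+FP), and adds an area under the curve.

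**The concern.** An accuracy study estimates how a test performs in a defined group, so the way patients are drawn from that group is part of the estimate. VP/(VP+FP) changes directly with prevalence. Sensitivity, specificity and AUC can change with the mix of mild and severe disease, and of clean and borderline normals.

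Eligibility here covers both suspected and known disease, with no quota and no consecutive rule. Who is approached can therefore alter the ratio of the two groups, and with it severity. Section 10.4 frames the sample size around severe coronary calcification, so the severity mix bears on the claim the study wants to make.

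Selection at enrolment cannot be repaired in the analysis. Without a log of eligible patients not enrolled, a reader cannot even compare the sample with the referrals it came from.

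**Working it through.** **1. Is there a planned figure to reproduce?** No. The protocol gives no expected sensitivity, specificity or prevalence, and the 200 in section 10.4 has no formula behind it. The point does not depend on the sample size.

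**2. Sampling text side by side.**
- 6.1: accuracy is claimed for stable patients with suspected or known disease.
- 7.1: the sample is one of convenience.
- 9.1: eligible patients are approached by the investigator or a collaborator. There is no requirement to invite consecutively and no log.

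Nothing connects the patients enrolled to all those eligible.

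**3. Timing text side by side.** Pointing to enrolment before the scan:
- 7.1 calls the study prospective.
- 8.1 requires an indication for a scan described as still to be done.
- 8.2 excludes rate or rhythm problems expected to degrade the images.
- 9.1 has patients consent to donate the image that will result.

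Leaving a gap: the word of sequence in 7.1 governs the study's own assessment of the images, not the scan or its clinical report. Section 9.2.4 speaks of donated images, which also fits scans already reported. No criterion in 8.1 or 8.2 bars a patient whose result is known. The order is implied but not stated as a rule.

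**4. How far could selection move the figures?** Every input below is assumed; none comes from the protocol.

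*Pooled value = sum of (share × stratum value).* Sensitivity is 0.50, 0.70 and 0.90 in mild, moderate and severe disease. Specificity is 0.85 in clean and 0.65 in borderline non-diseased patients.

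| Mix (mild/moderate/severe; clean/borderline) | Sensitivity | Specificity |
|---|---|---|
| No tilt: 50/30/20; 60/40 | 0.25 + 0.21 + 0.18 = 0.64 | 0.51 + 0.26 = 0.77 |
| Mild tilt: 40/30/30; 70/30 | 0.20 + 0.21 + 0.27 = 0.68 | 0.595 + 0.195 = 0.79 |
| Strong tilt: 20/30/50; 90/10 | 0.10 + 0.21 + 0.45 = 0.76 | 0.765 + 0.065 = 0.83 |

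The shifts are 4 and 12 points in sensitivity, and 2 and 6 points in specificity.

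*Two strata only (0.50 mild, 0.90 severe).* A 70/30 mix gives 0.35 + 0.27 = 0.62; a 40/60 mix gives 0.20 + 0.54 = 0.74. Read in reverse, selection towards mild disease lowers the figure by the same 12 points.

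*VP/(VP+FP) at sensitivity and specificity of 0.75 and prevalence p:* 0.75p / [0.75p + 0.25(1 − p)].
- p = 0.30: 0.225 / (0.225 + 0.175) = 0.56.
- p = 0.50: 0.375 / (0.375 + 0.125) = 0.75.

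If selection is unrelated to severity and to disease status, the mix is unchanged and every shift is zero.

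**The case against.** The strongest reply concerns timing. A reader might infer that sites will pick patients by their scan, or draw blood after a positive scan has already changed treatment. The documents do not support that. The cues in step 3 all describe a patient not yet scanned, and if the scan has not happened, staff cannot choose by its appearance. Section 8.2 also excludes vascular interventions in the previous 6 months. The manual of procedures promised in section 10.2 may fix the order of consent, blood draw and scan. This reply largely stands: on timing, what remains is an unwritten rule, which alone would be only a missing detail.

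Second, safeguards exist. Samples are sequenced only after enrolment ends (7.1), so no transcriptome result can influence who is enrolled. The calcium reader is blinded, and an external second reader is blind to the first reading (9.5). This is correct, but these measures protect the reading of images and the independence of the index test. They do not govern who is invited.

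Third, the study is exploratory. Aim III is worded as exploration, section 10.4 speaks of initial training, and the convenience sample is openly declared. That lowers the severity. It does not remove the point, because accuracy remains the primary objective and the better method costs little.

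Fourth, the illustrative sizes rest on invented inputs. True: they show that mixtures move averages, not that this study will be biased by any given amount.

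**Conclusion.** The point holds in a limited form. A convenience sample is stated for an accuracy objective, with no requirement to invite every eligible referral and no log. The accuracy figures may therefore not carry over to all stable patients referred for CCTA, and this could not be checked.

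Three stronger conclusions are tempting, and the protocol supports none of them:
- That the results do not apply to the stated population. Applicability is unverified, not disproved.
- That staff choice sets the disease spectrum. Referral practice and the long exclusion list in 8.2 shape it too.
- That accuracy will be inflated. The direction is unknown, because selection on features seen before the scan could go either way.

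Under the assumed values, shifts run from zero to about 12 points in sensitivity and 6 in specificity, and VP/(VP+FP) moves by about 19 points (0.56 to 0.75) for the prevalence change shown. These are illustrations, not estimates for this study. This is a cheap improvement to make before or during enrolment.

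**What to change.** - **Section 7.1:** replace the convenience sample with consecutive invitation of eligible CCTA referrals on recruiting days. Choosing the days remains a choice, but individual patients are no longer picked.
- **Section 9.1:** add that consent and blood draw take place before the CCTA result is known, and that the dates are recorded. If this is already the intended practice, it costs one sentence.
- **Section 9.1:** add an anonymous log of eligible patients not enrolled, with age, sex, suspected or known disease, and reason.

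The cost is somewhat less flexible or slower recruitment and the upkeep of a simple log at each site, which will take some staff time. No extra patients or study procedures are needed. The change only helps patients not yet enrolled, since selection already made cannot be undone.

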8.1. Inclusion Criteria

- Men and women between 18 and 75 years, with a clinical indication to be evaluated by a CCTA due to suspected or known CAD.
- Signature of informed consent.

8.2. Exclusion criteria.

- Previously known chronic renal or hepatic insufficiency.
- Active chronic lung disease, defined as: exacerbated asthma, exacerbated COPD, or pulmonary fibrosis.
- Myocardial infarction, unstable angina, cerebrovascular accident, or vascular interventions (any territory) in the past 6 months.
- Implantation of drug-eluting stents in the last 12 months.
- Revascularization surgery (By-pass)
- Indication of Angio-CT for congenital heart disease or Transcatheter Aortic Valve Replacement (TAVI)
- Presence/ diagnosis of heart failure symptoms or signs (ie. dyspnea, asthenia, edema) with objective evidence of pulmonary or systemic congestion at rest or with exercise in the last 6 months⁴³.
- Left ventricular ejection fraction <50% confirmed by objective diagnostic methods (eg doppler echocardiogram).
- Severe valvulopathies, confirmed by objective diagnostic methods (eg doppler echocardiogram).
- Uncontrolled hyper or hypothyroidism.

⁴³ "2013 ACCF/AHA guideline for the management of heart failure." <https://pubmed.ncbi.nlm.nih.gov/23741058/>. Accessed 10 Apr. 2023.

- Suprarenal insufficiency.
- Previous surgeries in the last 3 months.
- Severe trauma in the last 6 months, defined as one that involved bone fractures and/or surgical interventions.
- Known active cancer disease or under treatment (acute or preventive), or history of cancer disease without criteria for cure.
- Diagnosis of active autoimmune disease or any pathology under immunosuppressive treatment.
- Ongoing pregnancy, postpartum period of less than 12 months or breastfeeding.
- Other serious diseases with an estimated life expectancy of less than 12 months (according to the investigator's opinion).
- Temperature greater than 37.5°C recorded by a thermometer or any acute infection caused by viruses or bacteria confirmed by a health professional in the previous 30 days.
- Pacemaker/Cardio-Defibrillator Implantation.
- Prior to the study: heart rate > 70 l/m or atrial fibrillation or frequent extrasystoles that in the opinion of the specialist physician will affect the quality of the cardiovascular imaging.

9. Procedures

9.1. Eligibility and informed consent

Patients referred to CCTA scans with a medical indication due to suspected CAD or known CAD, will be recruited at Clínica Sagrada Familia and Sanatorio Mendez in Buenos Aires. Patients who meet the eligibility criteria will be approached by the main investigator or one of the study collaborators and the characteristics of the procedure to be performed, the risks of the associated procedures and the scope of the research to be

carried out will be explained to them. After providing the necessary information and answering the patients' questions, and once they have expressed that they agree to donate blood samples, mucose DNA cells via oral swab, associated data and the CCTA resulting image to the study, they will be formally invited to sign the informed consent.

9.2. Collection of clinical data and procedures in the baseline stage

At the time of inclusion in the study, the following epidemiological, clinical and complementary study data will be collected using questionnaires designed for this study:

9.2.1 Clinical data and medical history

- Contact data: Cell phone, landline, phone of an alternative contact, and E-mail address.
- Epidemiological data: date of birth, gender, ethnicity.
- Clinical history: Presence of any of the following pathologies: dyslipidemia, diabetes, high blood pressure, smoking, previous relevant diseases.
- Medications at the time of admission.

9.2.2 Peripheral blood sample

2.5 milliliters of peripheral blood will be obtained by puncture of the antecubital vein in a PAXgene or Tempus tube (commercial tubes that contain a solution for the preservation of RNA) to obtain RNA. The patient must fast for 8 hours prior to the study. Subsequently, the blood will be kept at room temperature for up to 48 hours, or at 4°C (in a refrigerator) for up to two weeks, until it is transferred to the laboratory, where it will be frozen at -20°C until it is processed (RNA extraction).

Subsequently, the second additional peripheral blood sample (10 milliliters in EDTA) will be obtained to measure the complete blood count, glycosylated hemoglobin, hepatogram, lipid profile, C-reactive protein and leukocyte formula. The primary tube for clinical laboratory analysis will be sent for analysis to local laboratories which are: Stamboulián and Sanatorio Méndez.

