5.1. In silico developments

In our laboratory, we have developed a comprehensive methodology for transcriptome analysis that combines extensive bioinformatic processing of biological samples with deep learning algorithms for interpretation. This approach enables the incorporation of all genes read in a sequence, performing classifications using a supervised method. Our algorithm has demonstrated robustness and high accuracy in preliminary tests.

The development consists of a pipeline that analyzes the RNA-seq sample in its crudest state, including coding and non-coding RNAs, circular RNAs, and the blood microbiome. The algorithm is trained on a cohort of previously classified samples and later validated using 10% to 20% of the samples.

To assess the algorithm's efficiency, we analyzed different RNA-seq databases available in digital repositories. Initially, we used the [GTEx database](#), containing 11,866 sequences from 30 different tissues obtained postmortem from dozens of individuals. Our algorithm achieved 99.1% accuracy in correct prediction (Figure 1), with only a few errors corresponding to potentially similar tissues (e.g., breast and fatty tissue).

Figure 1: Confusion matrix for normal tissue samples. The graph shows the intersection of the algorithm's prediction and the actual sample. Thus, the descending central diagonal from left to right shows the coincidence between the real and the predicted. Outside this diagonal, the numbers represent the algorithm's classification errors. As can be seen, they are infrequent.

We also analyzed the [Genomic Data Commons \(GDC\) database](#), containing RNA sequencing of biopsies from 34 different tumors with 10,000 samples. The algorithm's predictive capacity was again high, reaching 97.5% accuracy (Figure 2). These results demonstrate the algorithm's excellent classification capability for multiple samples.

Figure 2: Confusion matrix for tumor tissue samples. The graph has the same meaning as in the previous figure. Again, the number of mistakes outside the diagonal line is very low.

A sensitivity analysis of the algorithm was performed using 100 random samples from brain tumors in the GDC database. The algorithm achieved 100% precision (ROC of 1) and exhibited efficient behavior with a low number of clinical cases, reflecting the fundamental differences in gene expression between the two groups of tumors.

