9.2.4 Coronary Computed Tomography Angiography

Participants' donated CCTA images and associated data will be collected and anonymised at the site for further analysis.

CCTA acquisition protocols will follow each site's standard procedures. The use of any medications involved in routine CCTA examinations such as beta blockers (in the case of a heart rate higher than 65 beats per minute) or sublingual nitroglycerin will not be encouraged, the decision being left at the discretion of the physician involved in the acquisition. CTCA images will be transferred to an AWS server for independent data analysis.

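### RNA tube type and pre-freeze holding are neither fixed nor recorded, so if handling and disease prevalence both follow site, a pooled hold-out could not tell a site signature from a disease signal

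*Protocol*

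**What the plan says.** **Blood handling.** Section 9.2.2 allows collection "in a PAXgene or Tempus tube", after which "the blood will be kept at room temperature for up to 48 hours, or at 4°C (in a refrigerator) for up to two weeks", until transfer to the laboratory and freezing. It does not say who chooses, or whether the choice goes by site, day or patient. It does not ask for tube type, holding condition or times to be recorded, and the baseline data list in 9.2.1 has no such field. The preliminary work in 5.2 used PAXgene tubes only.

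**Reference label.** Section 9.2.4 states: "CCTA acquisition protocols will follow each site's standard procedures". Section 9.5 has calcium read by a blinded observer, with a second, external and blinded reading.

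**Sites.** Section 7.1 plans a convenience sample of 200 patients from "ENERI Medical Institute, La Sagrada Familia Clinic and Sanatorio Mendez". Section 9.1 says patients "will be recruited at Clínica Sagrada Familia and Sanatorio Mendez in Buenos Aires".

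**Validation.** Section 5.1 describes the pipeline: "The algorithm is trained on a cohort of previously classified samples and later validated using 10% to 20% of the samples". Specific aim III in 6.1 refers to a validation/test set without giving its size or how it is drawn. Sections 9.4 and 10.5 mention no split by site, no site adjustment and no external test set.

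**Laboratory timing.** Section 7.1 adds: "At the end of patient enrollment, biological samples will be sequenced".

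**The concern.** The primary objective is the diagnostic accuracy of a transcriptome classifier. Section 5.1 attributes the algorithm's sensitivity to about 200,000 gene variants, and this study applies it to 200 patients, or about 1,000 inputs per patient. A model that flexible can learn a technical signature as readily as a biological one.

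A technical signature becomes useful to the classifier when two things coincide: handling differs by site, and the frequency of the CT label differs by site. Enrolment is a convenience sample of patients with suspected or known CAD, and nothing controls that mix by site, so different prevalences are plausible. A hold-out drawn from the pooled samples contains the same sites, handled the same way, so it would reward the shortcut.

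Sensitivity, specificity and AUC would then overstate what the blood test knows about coronary disease. Handling that was not recorded at the draw may be impossible to recover later, so an analysis plan alone cannot repair this part.

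**Working it through.** **Inputs from the protocol.** 200 patients (7.1); hold-out of 10% to 20% (5.1, pipeline description); minimum of 150 for training (10.4); two or three sites (9.1, 7.1). **Assumed, because not given:** equal-sized sites, and the prevalence of the CT label at each site.

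**Step 1: split sizes.** 10% of 200 leaves 20 for testing and 180 for training; 20% leaves 40 and 160. Both keep at least 150 for training, so the 5.1 fraction is compatible with 10.4.

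**Step 2: AUC of a score that knows only the site.** For two equal sites with prevalences a ≤ b, the score calls everyone at the second site positive:

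- TPR = b / (a + b)
- FPR = (1 − b) / [(1 − a) + (1 − b)]
- AUC = 0.5 + (TPR − FPR) / 2

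| Assumed prevalences | TPR | FPR | Pooled AUC |
|---|---|---|---|
| equal | 0.50 | 0.50 | 0.50 |
| 45% vs 55% | 0.55 | 0.45 | 0.55 |
| 40% vs 60% | 0.60 | 0.40 | 0.60 |
| 20% vs 40% | 0.667 | 0.429 | 0.62 |
| 30% vs 70% | 0.70 | 0.30 | 0.70 |

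With three equal sites at 20%, 30% and 40%, the value is 0.61. Within any one site the score is constant, every case-control pair is tied, and the AUC is exactly 0.50. A within-site AUC therefore removes the contribution of site.

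**Step 3: what one small hold-out would show.** In 20,000 simulated hold-outs from two sites, a site-only score reached AUC 0.65 or more in these proportions:

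| Assumed prevalences | 20 patients | 40 patients |
|---|---|---|
| 30% at both sites | 13% | 4.5% |
| 20% vs 40% | 43% | 36% |

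Section 4.1 quotes 0.60–0.65 for traditional methods. That gives a sense of scale; the protocol does not make it a success threshold.

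**Step 4: is the remedy workable?** Assume two equal sites and 30% prevalence.

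- A within-site AUC from a 20-patient hold-out uses 3 × 7 = 21 case-control pairs per site, which is too few.
- From cross-validated predictions on all 200 patients it uses 30 × 70 = 2,100 pairs per site.
- Leave-one-site-out trains on 200 × 1/2 = 100 patients with two sites, or 200 × 2/3 ≈ 133 with three. Both are below the 150 in 10.4.

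**The case against.** The strongest reply is that the chain from handling to a false result is nowhere documented. This stands, and it sets the limit of the point. No section gives prevalence by site, and 9.2.2 ties neither tube nor holding condition to a site. The tubes contain an RNA preservative, and the documents do not show that holding within the permitted limits shifts expression. A reader might infer that sites will differ and that the accuracy result will be an artefact. The text supports only that this could happen unnoticed.

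Other objections also stand:

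- The 10% to 20% comes from the in silico section. A reader might take it as this study's fixed split, but aim III does not say so, and an SAP that is not among the documents may set the split and its stratification.
- The network reads the transcriptome, so CT acquisition is not a signal it can use directly. It can only shift the label, and adds to the problem only where label shifts and blood handling both follow site. Blinded double reading helps, but does not remove acquisition differences.
- Section 7.1 fixes only when sequencing takes place. It does not say that tubes stay frozen until enrolment ends, or that samples are processed in order of inclusion. Sequencing after enrolment in fact makes balanced batches possible.
- The two-versus-three-site conflict is a separate inconsistency. It does not itself show confounding.

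The objection does not answer the collection problem. The procedures manual planned in 10.2 could standardise or record handling, but the protocol it implements permits both tubes and both holding conditions.

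**Conclusion.** The point holds as an uncontrolled risk that should be closed before sampling. It is not a demonstrated bias. Two facts need no assumption: 9.2.2 leaves tube type and holding condition open and unrecorded, and 7.1 and 9.1 disagree on the number of sites. The consequence for accuracy is conditional on handling following site, on label prevalence differing by site, and on validation using a hold-out from the pooled samples.

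Under the first two conditions, with two equal sites, a site-only score adds nothing when prevalences are equal, about 0.05 in AUC above chance for a 10-point gap centred on 50%, 0.10 for a 20-point gap and 0.20 for a 40-point gap. Its within-site AUC is 0.50 in every case, so the two explanations can be separated if site and handling are recorded.

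**What to change.** 1. **Section 9.2.2:** use one tube type and one holding condition at all sites. At minimum, record tube type, holding condition, and draw and freeze date-times for every sample.
2. **Section 9.3:** randomise samples to extraction, library and sequencing batches, balanced by site and calcium category.
3. **Section 10.5, unless the SAP already does so:** stratify the training/test split by site. Beside the pooled AUC, report a within-site AUC (case-control pairs from the same site only, using cross-validated predictions over all 200 patients) and the AUC of a model given only site and handling variables. The second comparison is needed because a within-site AUC does not remove handling differences that arise inside a site. Treat leave-one-site-out as exploratory, since with equal sites it trains on fewer patients than the minimum in 10.4.
4. **Sections 7.1 and 9.1:** reconcile the site lists.

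**Cost:** a few data fields, a randomised batch list and some extra analysis, with no additional patients or assays. The within-site AUC will be less precise than the pooled one and may be lower.
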